In a 12-week, double-blind, placebo-controlled, multicenter study, 147 subjects with moderate to severe psoriasis were randomized to receive either an initial dose of 80 mg adalimumab followed by 40 mg adalimumab QOW, every week, or placebo ([Gordon, et al., 2006](#)). Subjects who completed the initial 12-week trial were eligible to continue in a 48-week extension trial. The primary efficacy analysis was the percentages of subjects achieving at least PASI-75 relative to baseline at Week 12 (for the initial trial) and at Week 24 (for the extension trial).

At 12 weeks, 53% of subjects receiving adalimumab QOW and 80% of subjects receiving adalimumab every week achieved PASI-75 compared to 4% of subjects receiving placebo (P<0.001).

Menter (Menter, et al., 2008) and Gordon (Gordon, et al., 2006) used the PASI-75 as the primary outcome measure with the PASI-75 evaluated at 16 weeks and 12 weeks, respectively. Both studies reported mean % change in PASI at Week 12: 76% Humira vs. 15% Placebo and 70% Humira vs. 14% placebo for Menter, 2008 and Gordon, 2006, respectively.

In this study (CHS-1420-02), eligible subjects are those who have a diagnosis of chronic PsO for at least 6 months that is moderate to severe as defined by a PASI score of greater than or equal to 12, Physician's Static Global Assessment (PSGA) score of greater than or equal to 3 (based on a scale of 0 to 5), and body surface area (BSA) affected by chronic PsO of greater than or equal to 10%. Subjects will be stratified by BMI < 30 kg/m² or ≥ 30 kg/m² and age < 65 years or ≥ 65 years (Menter, 2010).

The proposed dose level and dose regimen are consistent with that in the Humira (EU) Summary of Product Characteristics (AbbVie EU, 2014) and the Humira package insert (AbbVie US, 2014). In this study, 2 SC injections (2 pre-filled syringes, [80 mg]) of study drug will be administered on Week 0/Day 0. From Week 1/Day 7 through up to Week 23/Day 161, 1 SC injection (1 pre-filled syringe [40 mg]) of study drug will be administered QOW.

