4.3 Method of Assigning Subjects to Treatment Groups

Once the subject has signed the ICF at Screening, site personnel will assign a subject identification number (ID). The subject ID will include the site number (3 digits), and 3 digit subject number, assigned sequentially starting with 001. This number will be utilized to identify the subject throughout the study period. Once the subject ID has been assigned, the site will contact the Interactive Voice Response System/Interactive Web-based Response System (IXRS) to register the subject ID. Dropouts (subjects who discontinue study treatment early, and subjects who are randomized but not treated) will not be replaced. No individual is allowed to re-enter the study if previously randomized and dosed.

Subjects will be assigned to study drug in accordance with the randomization schedule generated using permuted block randomization by an independent statistician.

Approximately 500 subjects will be randomly assigned in a 1:1 ratio (approximately 250/arm) to receive 1 of the following treatments in Treatment Period 1:

- 2 SC injections (2 pre-filled syringes, [80 mg]) of Humira on Week 0/Day 0 and 1 SC injection (1 pre-filled syringe [40 mg]) of Humira QOW from Week 1/Day 7 through up to Week 15/Day 105.
- 2 SC injections (2 pre-filled syringes, [80 mg]) of CHS-1420 on Week 0/Day 0 and 1 SC injection (1 pre-filled syringe [40 mg]) of CHS-1420 QOW from Week 1/Day 7 through up to Week 15/Day 105.

Subject randomization will be stratified by body mass index (BMI) (less than ($<$) 30 kg/m² or greater than or equal to (\geq) 30 kg/m²), age (<65 yrs or ≥ 65 yrs) and region.

At the end of Treatment Period 1 (Week 16), subjects taking Humira will either begin dosing with CHS-1420 or continue with Humira during Treatment Period 2. A single randomization will be used to determine treatment in Treatment Periods 1 and 2. In effect, a 2:1:1 randomization will be used where for each 2 subjects randomized to receive CHS-1420 an additional 2 will be assigned to receive Humira in Treatment Period 1. For the subjects assigned to Humira in Treatment Period 1, 1/2 of these will be randomly assigned to continue with Humira for Treatment Period 2 and 1/2 will be assigned to switch to CHS-1420 for Treatment Period 2.

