7.2.3 Weight, Height, Body Surface Area and Body Mass Index

Weight (kg) and height (cm) will be measured at Screening. Subjects should be weighed wearing indoor, daytime clothing with no shoes. Before being weighed, subjects should empty their bladders.

In addition, weight will also be measured at Week 24, 32, 40 and 48 and, if the subject discontinues study participation, at the ET visit 56 days (8 weeks) after the last dose of study drug.

Body Mass Index should be calculated at screening using the method below:

English Units: $BMI = \text{Weight (lb)} / (\text{Height (in)} \times \text{Height (in)}) \times 703$

Metric Units: $BMI = \text{Weight (kg)} / (\text{Height (m)} \times \text{Height (m)})$

A web based calculator can be found at the following URL:

http://www.nhlbi.nih.gov/health/educational/lose_wt/BMI/bmicalc.htm

Body surface area (m^2) should be calculated at Screening using the Mosteller formula ([Mosteller, 1987](#)):

$$BSA (m^2) = \sqrt{(\text{Ht in cm} \times \text{Wt in kg}) / 3600}$$

A web-based calculator using the Mosteller formula may be found at the following URL: www.halls.md/body-surface-area/bca.htm. Make sure that the Mosteller formula is used to calculate BSA as this website offers several formulas.

Percentage of BSA affected by chronic PsO should be roughly estimated by using the subject’s palm size as roughly 1% of the total BSA and the BSA by body area used to assess PASI:

- Head and neck ~10%
- Upper extremities ~20%
- Trunk ~30%
- Lower extremities + buttocks ~40%

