8.2.2 Efficacy Analysis

The primary statistical analyses will be based on:

- The difference between the percentages of subjects in the CHS-1420 and Humira groups achieving PASI-75 at Week 12.

Equivalence will be based upon the 95% (2-sided) confidence interval for the difference in PASI-75 rates. If both the lower and upper bounds of the 95% confidence interval exclude $\pm 15\%$ (inclusive), equivalence will be established. The mean percent change in PASI from Baseline to Week 12 between the CHS-1420 and Humira (US) groups will be assessed as a supporting secondary endpoint.

Subjects who lack a PASI assessment at Week 12 will be considered non-responders in the primary analyses. As a sensitivity analysis, the last available score will be used.

For PASI-75 at Week 12 (as well as for other binary outcomes where formal evaluations are made, if applicable), Cochran-Mantel-Haenszel weights will be used to combine the stratum specific differences ([LaVange, Durham, & Koch, 2005](#)) formed by the randomization strata.

For the percent change in PASI from Baseline (as well as for other continuous outcomes where formal evaluations are made, if applicable), the stratum-specific differences will be combined using an analysis of variance approach with weights proportionate to the stratum sizes.

Other secondary continuous variables will be summarized using descriptive statistics (N, mean, standard deviation, 95% confidence interval, median, minimum, and maximum) and discrete variables will be summarized using frequency counts and percentages.

For data collected after the start of Treatment Period 2, data summaries for efficacy will be presented by the particular treatment sequence received in Treatment Periods 1 and 2: CHS-1420/CHS-1420, Humira/Humira and Humira/CHS-1420.

For data collected during the open label extension, only descriptive data summaries will be presented. These summaries will be presented by the particular treatment received in Treatment Period 2, regardless of treatment received in Treatment Period 1.

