8.3 Determination of Sample Size

Approximately 500 subjects will be randomized and treated for this trial (approximately 250 per arm in Treatment Period 1).

The sample size was determined to show comparable efficacy for the following endpoint based upon the PASI at Week 12:

- The percentages of subjects in each group, CHS-1420 and Humira, achieving PASI-75 at Week 12

For the proportion of subjects achieving a PASI-75, it has been assumed that 70% of subjects will be responders in both the reference group, Humira, and the CHS-1420 group. The sample size will produce 90% power to establish equivalence at the 5% alpha level (2-sided) with an equivalence margin of 15% (absolute). Subjects who lack a PASI assessment at Week 12 will be considered non-responders in the primary analyses.

The margin for equivalence has been based statistically on the study results from Menter (2008) and to a lesser extent Gordon (2006). At 12 weeks, Menter had PASI-75 responses of 68% (554/814) for Humira and 5% (20/398) for control. This results in a treatment effect of approximately 63% (absolute). A lower 95% confidence bound (2-sided) for the difference in response rates can be calculated to be 59%. The proposed 15% margin for demonstrating equivalence is much smaller than the demonstrated benefit associated with Humira.

Though Gordon (2006) was a considerably smaller study, at 12 weeks this study had similar PASI-75 responses of 71% (70/99) for Humira and 19% (9/48) for control. This results in a treatment effect of approximately 52% (absolute). Pooling Gordon and Menter using the method of Der Simonian and Laird, yields a lower bound on the treatment effect of at least 50% which also supports the use of a 15% equivalence margin.

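### The primary PASI-75 interval is valid, but adjusting only for the randomisation strata may give up a little precision that weight, age and baseline PASI could supply

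*Combined protocol and SAP*

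**What the plan says.** Section 8.2.2 sets the decision rule: "Equivalence will be based upon the 95% (2-sided) confidence interval for the difference in PASI-75 rates", with equivalence concluded if the interval lies within ±15 points. For PASI-75 at Week 12, "Cochran-Mantel-Haenszel weights will be used to combine the stratum specific differences", the strata being those of the randomisation. The Synopsis agrees. No baseline covariate is named for the primary PASI-75 comparison or for its last-available-score sensitivity analysis.

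Section 3.2 states "Subjects will be stratified by BMI" (cut at 30 kg/m²) and age (cut at 65 years). The Synopsis and Section 3.1 give the same two factors. Section 4.3 adds region as a third.

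Finer information exists for every subject. Section 7.2.3 says "Weight (kg) and height (cm) will be measured at Screening". Age is needed for eligibility and stratification. Section 6.1.1.1 defines baseline PASI as the last assessment before treatment at Week 0.

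On size, Section 8.3 plans about 250 per arm for 90% power, two-sided 5% alpha and a 15-point margin, and "it has been assumed that 70% of subjects will be responders in both the reference group, Humira, and the CHS-1420 group". It also says "Subjects who lack a PASI assessment at Week 12 will be considered non-responders in the primary analyses". It claims no credit for stratification or covariates.

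**The concern.** Equivalence depends on where the primary interval lies and how wide it is. If body size, age or initial severity predicts response, adjusting for it narrows the interval without recruiting anyone. Cutting a continuous measure in two discards part of what it predicts, and leaves chance imbalance within each half uncorrected. Baseline PASI is not used in the primary comparison at all.

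The plan itself treats BMI and age as worth stratifying on, under one fixed dosing regimen, so asking whether their measured values should be used is reasonable. Extra precision would be worth most if the true response rate is below 70% or the true difference is not exactly zero.

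**Working it through.** **Inputs from the documents.** Response 70% in both arms, margin 15 points and a 95% two-sided interval (Sections 8.2.2 and 8.3); 250 per arm (Section 4.3).

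**Input not in the documents.** R², the share of outcome variance that baseline measures explain beyond the strata. It is assumed, and a range is shown.

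**Step 1: reproduce the planned size.**
- n per arm = 2p(1−p)(z₀.₉₇₅ + z₀.₉₅)²/margin² = 2 × 0.70 × 0.30 × (1.960 + 1.645)²/0.15² = 242.6, so 243. The plan has about 250.
- SE at 250 per arm = √(2 × 0.21/250) = 0.0410.
- Power at zero difference = 2Φ(0.15/0.0410 − 1.96) − 1 = 91.1%. The stated 90% is confirmed.

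**Step 2: effect of extra R².** SE is multiplied by √(1−R²). With true difference d, power = Φ((0.15−d)/SE − 1.96) + Φ((0.15+d)/SE − 1.96) − 1. The variance is held at its 70% value throughout. The unadjusted size that gives the same precision is 250/(1−R²).

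| Extra R² (assumed) | Half-width (points) | Power, d = 0 | Power, d = 3 points | Equivalent n per arm |
|---|---|---|---|---|
| 0 | 8.03 | 91.1% | 82.6% | 250 |
| 0.005 | 8.01 | 91.3% | 82.8% | 251 |
| 0.014 | 7.98 | 91.6% | 83.2% | 254 |
| 0.027 | 7.92 | 92.0% | 83.7% | 257 |
| 0.03 | 7.91 | 92.1% | 83.8% | 258 |
| 0.06 | 7.79 | 93.0% | 85.0% | 266 |

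**Step 3: which rows are plausible.** Two simulations used assumed associations.
- *Weight beyond a median BMI split* (200,000 subjects, assumed weight–BMI correlation 0.85). Odds ratios per SD of 0.8, 0.7 and 0.6 gave 0.6%, 1.4% and 2.7% less variance. A second, severity-type covariate (odds ratios 1.2, 1.3 and 1.5 respectively) brought these to 1.2%, 2.6% and 5.7%.
- *CMH over BMI at 30 and age at 65, against logistic standardisation on continuous values* (3,000 trials of 500; BMI mean 31, SD 6.5 and age mean 45, SD 13, all assumed). BMI with at most a weak age effect gave an extra R² of 0.003 to 0.014. In the two runs with a further prognostic measure, theoretical R² was 0.035 and 0.076. The simulated SE ratios were 0.9794 and 0.9752, so the variance reductions realised were 1 − 0.9794² = 4.1% and 1 − 0.9752² = 4.9%.

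Taken together, weight and age give roughly 0.5% to 3%, and adding a severity measure roughly 1% to 6%.

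**Step 4: a lower response rate.** At an illustrative 65% in both arms and zero difference, the same formula gives 88.0% with no extra R², 89.3% at R² = 0.03 and 90.4% at R² = 0.06.

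**The case against.** The strongest reply is that nothing here is wrong. The CMH-weighted difference is prespecified, reflects the randomisation and follows a cited paper on randomisation-based nonparametric methods, so avoiding an outcome model may be deliberate. Power already exceeds 90% on the plan's assumptions, and stratification handles the coarser imbalance in body size and age. All of that stands.

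A reader might infer that the interval is defective, or that the trial is underpowered for want of covariates. The documents support neither: the interval is valid, and the stated size reproduces without any adjustment.

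A reader might also infer that using BMI or weight and age uncut would by itself buy a material gain. Under the assumptions tried it would not: at most about 0.12 points of half-width (8.03 to 7.91). The larger figures require a severity measure as well.

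Nor does stratifying on BMI and age show how strongly they predict PASI-75. No section gives that association, so a flat statement that precision is lost goes too far.

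Finally, the standardised and CMH-weighted differences agree closely under 1:1 stratified allocation but need not coincide if the effect varies across strata. That is a reason to fix the choice in advance, not to avoid adjustment.

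**Conclusion.** The point holds as a small, nearly free improvement. The primary analysis uses BMI and age only as two classes each and leaves baseline PASI out, so it may give up some precision on the interval that decides the trial.

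At 70% response and 250 per arm, continuous weight and age might raise power from 91.1% to about 91.3–92.1% at zero difference, and from 82.6% to about 82.8–83.8% at a 3-point difference. With baseline PASI added, power might reach about 93% at zero difference. These figures rest on assumed prognostic strengths and assumed covariate distributions. If the measures do not predict response, the gain is nil.

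A separate matter needs settling whichever analysis is kept. The randomisation strata are not uniquely defined, because region appears in Section 4.3 but not in the Synopsis, Section 3.1 or Section 3.2.

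**What to change.** In Section 8.2.2, keep the endpoint, the Full Analysis Population, the non-responder rule and the 15-point margin. Then:

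- Estimate the marginal difference in PASI-75 rates by standardisation from a logistic model with treatment, the randomisation strata, and Screening weight, age and baseline PASI as continuous covariates.
- Name one robust variance method for the 95% interval before unblinding.
- Keep the CMH-weighted difference as the supporting analysis, and as the named fallback if the model does not converge.
- State which strata apply, and reconcile Section 4.3 with the Synopsis and Sections 3.1 and 3.2 on region.

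The cost is SAP wording and modest programming, with no new data or subjects. The downside is a slightly less simple primary analysis.

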Study Design	
This is a 55-week (including follow-up), randomized, double-blind, active-control, parallel-group, multicenter, global study in subjects with active, moderate to severe, chronic PsO.
 
The study will consist of 23 weeks of administration of blinded study drug over a 24 week period, divided into Treatment Period 1 and Treatment Period 2, followed by 23 weeks of administration of open-label CHS-1420 (Treatment Period 3) over a 24 week period and a Follow-up (or Early Termination [ET]) visit 8 weeks after the last dose. Subjects who meet inclusion/exclusion criteria will be stratified by body mass index (BMI) less than ($<$) 30 kg/m² or greater than or equal to (\geq) 30 kg/m², and age <65 yrs or ≥ 65 yrs and randomized 1:1 to receive CHS-1420 or Humira in Treatment Period 1. Subjects assigned to CHS-1420 will continue to receive CHS-1420 in Treatment Period 2. Subjects assigned to Humira in Treatment Period 1 will be randomly assigned (1:1) to either continue with Humira in Treatment Period 2 or to switch to CHS-1420 in Treatment Period 2.
 
In Treatment Period 1, subjects will receive 2 subcutaneous (SC) injections of study drug on Week 0/Day 0 followed by single SC injections of study drug every other week (QOW) from Week 1/Day 7 through Week 15/Day 105
 
For Treatment Period 2, subjects assigned to Humira in Treatment Period 1 will be switched to either CHS-1420 or continue with Humira, and will continue to receive single SC injections of study drug QOW from Week 17/Day 119 through Week 23/Day 161.
 
All subjects that complete Treatment Periods 1 and 2 and achieve at least a 50% improvement in PASI score (PASI-50) at Week 24 will receive 23 weeks of open-label CHS-1420 in Treatment Period 3 QOW from Week 25/Day 185 through Week 47/Day 329.
 
The first dose of study drug on Week 0/Day 0 will be self-administered or administered by a caregiver at the investigative site, and subjects will be monitored for adverse reactions and injection site reactions (ISRs) during the 2 hours after this dose. Subsequent doses will be self-administered or administered by a caregiver at home. Subjects/caregivers will be trained on

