	
For confidence interval involving binary outcomes, the Cochran-Mantel-Haenszel weights will be used to combine the stratum-specific differences where the strata will be based upon the factors used to assign subjects to treatment for involving continuous outcomes, the stratum-specific differences will be combined using an analysis of variance approach with weights proportionate to the stratum sizes.
 
Other secondary continuous variables will be summarized using descriptive statistics (N, mean, standard deviation, 95% confidence interval, median, range, minimum, and maximum, where appropriate). Discrete variables will be summarized using frequency counts and percentages.
 
Starting with Treatment Period 2, data summaries for efficacy will be presented by the particular treatment sequence received in Treatment Periods 1 and 2: CHS-1420/CHS-1420, Humira/Humira and Humira/CHS-1420. Safety data for Treatment Period 1 will be presented by the treatment received. Safety data for the study period as a whole (ie, time spanning Treatment Periods 1 to 3) will be presented for those randomized and receiving the same treatment in Treatment Periods 1 and 2. Separate summaries will be presented for Treatment Period 2 based upon the particular treatment sequence received in Treatment Periods 1 and 2: CHS-1420/CHS-1420, Humira/Humira and Humira/CHS-1420. Safety data for the open-label extension (Treatment Period 3) will be summarized based primarily upon events first recorded (or worsened in severity) during the open-label extension.

Study Duration	
Screening: up to 28 days
 
Treatment Period 1: 16 weeks (Week 0 to Week 16)
 
Treatment Period 2: 8 weeks (Week 17 to Week 24)
 
Treatment Period 3: 24 weeks (Week 25 to Week 48)
 
Follow-up: 8 weeks after last dose of study drug
 
Subjects may be considered completers if the subjects complete 48 weeks of treatment and the Follow-up visit 8 weeks following the last dose in this trial (completes the study);
 
Subjects may be withdrawn from study therapy for any of the following reasons:
 
• The subject experiences a serious adverse event (SAE) or medically important AE (e.g., serious or opportunistic infection) that would preclude further treatment with study drug;

[figure not shown]

Figure 1: Study Design

[figure not shown]

TABLE OF CONTENTS

SYNOPSIS	4
TABLE OF CONTENTS	13
LIST OF TABLES	15
LIST OF FIGURES	16

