3 INVESTIGATIONAL PLAN

3.1 Overall Study Design and Plan

This is a 48 week study with a follow up visit 8 weeks after the last dose, randomized, double-blind, active-control followed by open label safety, parallel group, multicenter, study in subjects with active, moderate to severe, chronic PsO. Approximately 500 subjects will be randomized at approximately 160 sites worldwide.

The study will consist of 23 weeks of administration of blinded study drug over a 24 week period, divided into Treatment Period 1 (16 weeks) and Treatment Period 2 (8 weeks), 23 weeks of open label CHS-1420 during 24 weeks of Treatment Period 3 and a Follow-up visit 56 days (8 weeks) after the last dose of study drug. Subjects who meet inclusion/exclusion criteria will be stratified by body mass index (BMI) < 30 kg/m² or ≥ 30 kg/m² and by age < 65 years or ≥ 65 years. Within these strata, subjects will be randomized to receive either CHS-1420 or Humira. Half of the subjects assigned to Humira will be assigned to receive CHS-1420 in Treatment Period 2 with the remainder continuing on Humira. For simplicity, the assignments for Treatment Period 1 and Treatment Period 2 will be made at the beginning of Treatment Period 1.

In Treatment Period 1, subjects will receive 2 subcutaneous (SC) injections of study drug on Week 0/Day 0 followed by single SC injections of study drug every other week (QOW) from Week 1/Day 7 through Week 15/Day 105.

For Treatment Period 2, subjects will: 1) continue on CHS-1420 or 2) Humira or 3) will be switched from Humira to CHS-1420 and they will continue to receive single SC injections of study drug QOW from Week 17/Day 119 through Week 23/Day 161.

For Treatment Period 3, all subjects that complete Treatment Periods 1 and 2 and achieve at least a 50% improvement in PASI score (PASI-50) at Week 24 will receive 23 weeks of open-label CHS-1420 in Treatment Period 3 QOW from Week 25/Day 185 through Week 47/Day 329.

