6 EFFICACY MEASUREMENTS

6.1 Efficacy Variables

6.1.1 Primary Efficacy Variable

The primary efficacy endpoint is:

- 75% improvement in Psoriasis Area and Severity Index (PASI-75) at Week 12 relative to Baseline, where Baseline will be the last assessment prior to beginning study drug (scheduled for Week 0/day 0)

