6.1.1.1 Psoriasis Area and Severity Index

The PsO lesions are scored on a scale of 0 to 4 for 3 characteristics: erythema, infiltration, and desquamation, weighted by the area of involvement ([Fredriksson & Pettersson, 1978](#)) ([Feldman & Krueger, 2005](#)). The lesions are scored within 4 anatomical regions: head, upper extremities, trunk, and lower extremities including buttocks. Within each of these regions, the area of involvement is scored on a scale of 0 to 6. The clinician will assess the subject's PsO lesions according to the PASI at Screening, Week 0/Day 0, and at the Week 2, 4, 6, 8, 10, 12, 16, 20, 24, 32, 40 and 48 visits, as well as at the ET and FU visit, as applicable. The Baseline value will be the last PASI assessment prior to receiving treatment at Week 0/Day 0. The clinician will determine PASI score at Screening and confirm that the PASI score still meets the inclusion criterion at Week 0/Day 0 (pre-randomization). Whenever possible, the same Investigator/Clinician or trained PASI assessor should conduct the PASI assessment for each subject at each visit.

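### Percent change in PASI at Week 12 is analysed without baseline PASI as a covariate, which may give up a little precision on a supporting secondary endpoint

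*Combined protocol and SAP*

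**What the plan says.** Section 8.2.2 gives the Week 12 comparison of mean percent change in PASI a limited role: it "will be assessed as a supporting secondary endpoint". No margin, SD or power is stated for it. For this endpoint, and for any other continuous outcome that is formally evaluated, "the stratum-specific differences will be combined using an analysis of variance approach with weights proportionate to the stratum sizes". The Statistical Analysis part of the Synopsis gives the same method. Neither place names a covariate or a rule for sparse strata.

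Baseline PASI is collected by design. Section 6.1.1.1 has the clinician score PASI at Screening and "confirm that the PASI score still meets the inclusion criterion at Week 0/Day 0 (pre-randomization". Section 5.2.2 lists the same step among the procedures that precede randomisation. Section 6.1.1 defines the reference value: "where Baseline will be the last assessment prior to beginning study drug".

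The strata are described in two ways:
- **BMI and age only.** The Synopsis has subjects "stratified by body mass index (BMI) less than" or at least 30 kg/m², and by age. Section 3.1 lists the same two factors and adds: "Within these strata, subjects will be randomized to receive either CHS-1420 or Humira". Section 3.2 also lists only these two.
- **BMI, age and region.** The list in Section 4.3 ends "65 yrs) and region".

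The Synopsis says that "the strata will be based upon the factors used to assign subjects to treatment". The number of regions, the block size and the expected share aged 65 or older are not given.

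**The concern.** A covariate measured before randomisation on every subject can only help the precision of a continuous comparison in a trial of this size, apart from the trivial loss of one degree of freedom. Leaving it out gives an interval at least as wide as the collected data allow. What is at stake is the width of the CI around the one continuous result that is meant to support the PASI-75 conclusion.

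There is a second, conditional point. A weight proportional to stratum size stays positive when one arm of a stratum has no observed subjects, yet that stratum's difference does not exist. The estimator as worded then has no value, and the analyst would have to choose a fallback after seeing the data.

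**Working it through.** **The plan's own figure.** None is stated for percent change in PASI. The only nearby figure is the primary sample size in Section 8.3: 70% responders in both arms, margin 15 points, 95% CI, 250 per arm, 90% power. Two one-sided tests give n = 2(0.7)(0.3)(1.960 + 1.645)²/0.15² = 243 per arm. At 250 per arm, power = 2Φ(0.15/√(0.42/250) − 1.96) − 1 = 91.1%. The stated figure reproduces, and this point does not affect it.

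**Precision from a baseline covariate.** Inputs: 250 per arm (Section 8.3). Assumed, because the documents give neither: SD of percent change 20, 30 or 40 points; correlation r of baseline PASI with percent change 0 to 0.3.

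- Unadjusted SE = SD × √(2/250). At SD 30 this is 2.683, so the half-width is 1.96 × 2.683 = 5.26 points.
- Adjusted half-width = unadjusted half-width × √(1 − r²).
- Equivalent extra subjects = 500/(1 − r²) − 500.

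| r | √(1 − r²) | Half-width, SD 20 | SD 30 | SD 40 | CI narrower by | Extra subjects |
|---|---|---|---|---|---|---|
| 0 | 1.000 | 3.51 | 5.26 | 7.01 | 0% | 0 |
| 0.1 | 0.995 | 3.49 | 5.23 | 6.98 | 0.5% | 5.1 |
| 0.2 | 0.980 | 3.44 | 5.15 | 6.87 | 2.0% | 20.8 |
| 0.3 | 0.954 | 3.34 | 5.02 | 6.69 | 4.6% | 49.5 |

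**Empty arms.** For a stratum with n1 and n2 observed subjects, the size weight is n1 + n2 and the CMH weight is n1·n2/(n1 + n2). With 3 against 0, the size weight is 3 on a difference that does not exist; the CMH weight is 0, so the stratum drops out. The PASI-75 analysis is therefore protected by its own weights.

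How often this could happen was simulated for 500 subjects under permuted blocks and equal-sized regions. Two sets of assumptions were used: (i) BMI split 50/50, blocks of 4, 0 to 10% missing Week 12 PASI; (ii) 45% with BMI of 30 or more, blocks of 4 or 8, 8% missing.

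- **BMI by age (4 strata):** (i) 0 to 0.1% when 5 to 15% are 65 or older, 2 to 3% when 3% are, 13 to 16% when 2% are. (ii) At most 0.2% when 5% or more are, 3.5 to 6.8% when 3% are.
- **Three regions (12 strata):** (i) 50 to 60% at a 65+ share of 5%, 0.1% at 15%. (ii) 60 to 73% at 5%, under 1% at 15%.
- **Five regions (20 strata):** (i) 97 to 98% at 5%, 8 to 17% at 15%.

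**Behaviour of the replacement model.** A further simulation used 1, 3 or 5 regions, a 65+ share of 5% or 12%, r of 0.1 to 0.3, SD 30, 5% missing, and no treatment-by-stratum interaction. Main-effects ANCOVA was estimable in all 6,736 runs in which the size-weighted estimate was undefined, and its 95% CI coverage was 94.0 to 96.4%. Changing the weighting alone, before baseline is added, moved the estimate by 0.02 to 0.15 points on average, against an SE of about 2.75.

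**The case against.** The best case for the plan is that nothing here is wrong. A stratified comparison without a covariate is valid in a randomised trial, and nothing in the documents promises ANCOVA. Percent change already divides by baseline, so the remaining correlation may be close to zero, where the gain is nil. All of this stands. It limits the size of the point but does not remove it, because the covariate is already collected.

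The replacement also has a price. The size-weighted estimator targets the average effect over strata without assuming that the effect is the same in each, whereas a main-effects model summarises a common effect. The simulation assumed no interaction, so it cannot show that cost. This stands, and is met by keeping the size-weighted estimate as a sensitivity analysis. The change also does not settle how a missing Week 12 percent change is handled, which is a separate matter.

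On empty arms, three of the four places that list the factors omit region. With blocks of 4, before dropout, only a stratum of at most 2 subjects (2/500 = 0.4% of the sample) can have an empty arm, so pooling or dropping it would hardly move the estimate. In Section 8.2.2 the randomisation strata are named in the sentence on binary outcomes; the sentence on continuous outcomes does not define its own. The point is therefore secondary and conditional.

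A reader might infer three stronger things that the documents do not support:
- **That baseline PASI is ignored.** It is not: it is the denominator of the endpoint. It is absent only as a covariate.
- **That uncorrected chance imbalance in baseline is a further harm.** It is the same effect as the lost precision, and the unadjusted CI already covers it.
- **That the equivalence conclusion is at risk, or that this analysis will probably fail.** The decision rests on PASI-75 with CMH weights, and the high empty-arm percentages need both region as a factor and a small 65+ share, neither of which is established.

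**Conclusion.** The point holds as a modest, low-cost improvement. The planned analysis causes no bias, and the primary analysis and sample size are untouched. The possible gain is a 95% CI 0 to 4.6% narrower, or 0 to 0.24 points off a half-width of 5.26 at SD 30 (5.26 − 5.02 = 0.24). It rests on an assumed correlation of 0 to 0.3 that the documents neither give nor contradict; at zero there is no gain.

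The undefined-estimator point is correct as algebra. Its likelihood is negligible under BMI by age strata unless very few subjects are 65 or older, and becomes material only if region was used. The conflict between Section 4.3 and the Synopsis, Section 3.1 and Section 3.2 needs to be resolved in any case, because the same factors define the strata for the primary CMH analysis.

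**What to change.** In Section 8.2.2 and the Synopsis, state that percent change in PASI at Week 12 will be analysed by ANCOVA with treatment, baseline PASI and the stratification factors actually used as main effects, reporting the adjusted mean difference with its 95% CI. Keep the size-weighted stratum estimate as a sensitivity analysis, with a stated rule for pooling or dropping any stratum with an empty arm. Leave the CMH analysis of PASI-75 as it is. Make the factor lists in the Synopsis and Sections 3.1, 3.2 and 4.3 match the randomisation schedule.

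The cost is a sentence or two in each of the two analysis descriptions and a correction to the factor lists. No new data, visits or subjects are needed: PASI, BMI and age are already collected before randomisation, and region is known from the site. The statistical cost is the common-effect reading of the main-effects model, which the sensitivity analysis covers.
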